9.3 Exploratory Endpoints

9.3.1 Exploratory Efficacy Endpoints

- Severity assessment of first episodes of virologically-confirmed (RT-PCR positive) cases of COVID-19 meeting the case definition for the primary efficacy analysis.
- The following endpoints are analyzed as occurring ≥ 15 days after the second trial vaccination (full VE).
 - In SARS-CoV-2 naïve subjects:
 - Occurrence of supplemental oxygenation due to COVID-19.
 - Occurrence of mechanical ventilation due to COVID-19.
 - Occurrence of hospitalization due to COVID-19.
 - Occurrence of death due to COVID-19.
 - Occurrence of death due to any cause.

Thereby, the start date of the COVID-19 case leading to occurrence of any of the above must be ≥ 15 days after second trial vaccination.

9.3.2 Exploratory Immunogenicity Endpoints

On Days 1, 29, 43, 120, and 211 in peripheral blood mononuclear cells (PBMCs) from approximately 200 subjects at selected site(s):

- The frequency and functionality of SARS-CoV-2 RBD of S-specific T-cell response after antigen stimulation by intracellular cytokine staining (ICS) to investigate Th1 response and expression of Th2 markers.
- The proportion of subjects with a detectable increase in SARS-CoV-2 RBD of S-specific T-cell response.

Thereby, testing of samples collected on Day 120 and Day 211 is done only in subjects categorized as T-cell responders on Day 29 and/or Day 43. First testing of samples is performed for a subset of these 200 subjects and might be extended to 200 subjects if T-cell response is detectable.

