For the primary analysis of efficacy, COVID-19 case ascertainment begins at \geq 15 days following the second vaccination of CVnCoV. This time point allows the immune response to mature and reach its full height following the second dose. As such, case ascertainment starting at this time point represents the evaluation of full VE of CVnCoV against COVID-19.

The safety objective of Phase 3 is to generate a large-scale safety database that will demonstrate the safety of CVnCoV. All subjects participating in the Phase 2b and observer-blinded Phase 3 parts of the trial will have medically-attended AEs collected for 6 months after the second vaccination; and AESIs and SAEs collected for 1 year after the second vaccination. As such, each subject will participate in the trial for approximately 13.5 months for the safety follow-up.

Individuals with history of virologically-confirmed COVID-19 illness will be excluded from participating in this trial. However, this trial will not screen for or exclude subjects with history or laboratory evidence of prior SARS-CoV-2 infection, many of which might have been asymptomatic. Because pre-vaccination screening for prior infection is unlikely to occur in practice, it is important to understand vaccine safety and COVID-19 outcomes in in individuals with prior infection with SARS-CoV-2 virus.

CMI will be evaluated in approximately 200 subjects: 100 who receive CVnCoV and 100 who receive placebo. The goals of this are to identify immunological biomarkers to identify vaccine responders and people having a better immune response to CVnCoV, to better understand the biology of the immune response to CVnCoV, and to investigate the duration of the immune response to CVnCoV. Analysis of immunologically relevant genomic biomarkers will be limited to DNA sequencing of the subject's T-cell receptor and human leukocyte antigen type. The purpose is not to test for any genetic disorders or to identify predisposition to any disease.

Open-label Phase

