
On Days 1, 29, 43, 120, and 211 in PBMCs from up to 200 subjects at selected site(s):
 
 • The frequency and functionality of SARS-CoV-2 RBD of S-specific T-cell response after antigen stimulation by ICS to investigate Th1 response and expression of Th2 markers. • The proportion of subjects with a detectable increase in SARS-CoV-2 RBD of S-specific T-cell response. 
Thereby, testing of samples collected on Day 120 and Day 211 is done only in subjects categorized as T-cell responders on Day 29 and/or Day 43. First testing of samples is performed for a subset of these subjects and might be extended to 200 subjects if T-cell response is detectable.
	
In subjects belonging to the Immunogenicity/Reactogenicity subset and selected to take part of the CMI subset:
 
 • The number and percentage of subjects for whom a SARS CoV-2 RBD of S-specific T-cell response is observed • The number and percentage of subjects with a detectable increase in SARS-CoV-2 RBD of S-specific T-cell response

Table 2: Study Endpoints and Estimands for the Open Label Phase (Scenario A only)

Safety	

 Occurrence, intensity and relationship of SAEs and AESIs collected throughout the trial until the EOT. Occurrence of fatal SAEs throughout the trial until the EOT. Occurrence of AEs leading to trial discontinuation. 	
In subjects who received at least 1 dose of CVnCoV and participate in the open-label phase of the trial:
 
 SAE after the first dose with an AV in the open-label phase until the EOT. AESI after the first dose with an AV in the open-label phase until the EOT. Fatal SAE in the open-label phase through EOT. At least 1 AE leading to trial discontinuation.
Exploratory Efficacy	

 Occurrence of first episodes of symptomatic virologically-confirmed (RT-PCR positive) cases of COVID-19 of any severity as assessed by the Investigator. 	
In naïve subjects from the Open-Label Set (OLS) at any time after the first vaccination:
 $VE = 1 - RR \text{ with exact 95\% CI}$ 
Where RR is the ratio of attack rates of COVID-19 cases per 100 person-month in Cohort A: CVnCoV-AV over Cohort B: CVnCoV only.

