*** RESTRICTED TO SUBJECTS WITH CMI ASSESSMENTS PERFORMED**
\$ ALL SAFETY ENDPOINTS ARE ANALYSED FOR ALL SUBJECTS, IN SUBJECTS SERONEGATIVE AT BASELINE, AND IN SUBJECTS SEROPOSITIVE AT BASELINE

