10.6.3 Cell-mediated Immunity

CMI is evaluated in approximately 200 subjects in selected sites.

The frequency and functionality of SARS-CoV-2 RBD of S-specific T-cell response after antigen stimulation is determined in PBMC in comparison to baseline. CMI assessment is performed on Day 1 (baseline), Day 29, Day 43, Day 120 and Day 211. Note that testing on Day 120 and Day 211 is only performed on subjects who are determined as T-cell responders on Day 29 and/or Day 43.

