12.0 Statistical Methods

Unless otherwise noted, categorical variables are summarized using counts and percentages. Percentages are presented with one decimal place, except for 100% which is displayed without any decimal places and percentages are not displayed for zero counts. Continuous variables are summarized using the number of observations (n), mean, median, SD, 1st Quartile (Q1), and 3rd Quartile (Q3), minimum and maximum values. Mean, median, Q1 and Q3 are presented to 1 decimal more than original data. SD is presented with 2 decimals more than original data. Minimum and maximum match the decimal points in the original data. The maximum number of decimals is 4, unless otherwise stated.

In general, for the blinded study phase, all data summaries are presented overall and by vaccine group. Summaries are further repeated by age group (18 to 60 years and ≥ 61 years) and vaccine group. Efficacy outputs do not have an overall column presented. Selected outputs are additionally presented using further subsetting of the data. This is specified explicitly in the respective sections. Data summaries for the OL-phase are generally presented by cohort, unless otherwise stated.

If not stated otherwise, p-values from statistical tests are two-sided and CIs are calculated using a 95% confidence level.

The factors used for stratification of randomization are age group and country. The primary and key secondary efficacy analyses are not adjusted for these factors, but the analyses are repeated by age group (18 to 60 years and ≥ 61 years) and by country separately. The sensitivity analyses for the primary endpoint using time to event methodology includes both stratification factors in the statistical model.

No imputation of missing data other than that described in Section 10.3 is performed.

All data collected during this trial is displayed in data listings, unless otherwise specified. Screening failures are excluded from all listings and tables if not otherwise stated. Listings include all relevant assigned/derived variables. If not explicitly stated, listings do not show imputed data, but present data as reported.

All data summaries and tabulations are prepared using SAS® Version 9.4 or higher.

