12.8.2 Exploratory Immunogenicity Analyses

CMI assessments are performed in IS subjects from selected sites. The frequency of immune cell populations induced by the vaccine is summarized at each post-baseline timepoint.

Further characterization of the T-cell immune response may be done with other technologies like ELISpot, CyTOF and/or analysis of genomic biomarkers.

All relevant data is presented in listings.

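### Day 120 and Day 211 T-cell results come only from early responders but are summarised in the same visit series as Days 29 and 43, so the late frequencies understate waning and the late arms are not randomised groups.

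*SAP*

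**What the plan says.** The cell-mediated immunity (CMI) work covers about 200 subjects, 100 per arm (SAP 8.1; Protocol 5.2 and 9.4.4). SAP 9.3.2 sets two exploratory endpoints over Days 1, 29, 43, 120 and 211: the frequency and functionality of the T-cell response, and the proportion with a detectable increase. Late testing is restricted in the same section: "testing of samples collected on Day 120 and Day 211 is done only in subjects categorized as T-cell responders" at Day 29 and/or Day 43. SAP 10.6.3 repeats the rule: "testing on Day 120 and Day 211 is only performed on subjects who are determined as T-cell responders on Day 29 and/or Day 43". Protocol 9.4.4 says the same.

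On analysis, SAP 12.8.2 states: "The frequency of immune cell populations induced by the vaccine is summarized at each post-baseline timepoint". SAP 12.0 presents blinded-phase summaries by vaccine group. The estimand in SAP 9.5 is "The number and percentage of subjects with a detectable increase in SARS-CoV-2 RBD of S-specific T-cell response", within the CMI subset, with no denominator per visit. The analysis set (SAP 9.6.9, Table 4) is the PPI set with the footnote "RESTRICTED TO SUBJECTS WITH CMI ASSESSMENTS PERFORMED". On missing data, SAP 12.0 says "No imputation of missing data other than that described in Section 10.3 is performed", and Section 10.3 has no rule for CMI samples left untested by design.

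Neither document labels the late results as applying to early responders, and neither gives a numerical definition of a T-cell responder. Protocol 5.2 names as one goal of the CMI work "to investigate the duration of the immune response to CVnCoV".

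**The concern.** Days 29 and 43 are assayed in every subject entered for testing. Days 120 and 211 are assayed only in those who already responded, so the late population is chosen on the outcome being measured. A table or plot that runs through the visits compares different populations, and part of any change from Day 43 to Day 211 is the change in who was tested.

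Duration of the cellular response is a stated purpose, and Days 120 and 211 are the visits that address it. The antibody endpoints use the same visits without responder selection, so a reader would naturally take the T-cell table to be built the same way. The late placebo column holds only placebo subjects classed as early responders, so randomisation no longer supports a comparison between the arms at those visits.

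**Working it through.** The plan states no responder rate, power or expected persistence for CMI, so there is no figure to reproduce. All rates below are assumptions used to show direction and range.

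**1. Who contributes at each visit**

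| Visit | Tested population | Source |
|---|---|---|
| Days 1, 29, 43 | all subjects entered for CMI testing | SAP 9.3.2 |
| Days 120, 211 | responders at Day 29 and/or 43 only | SAP 9.3.2, 10.6.3 |
| Summary | every post-baseline visit, by vaccine group | SAP 12.8.2, 12.0 |

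**2. Responder percentage**

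Let R be the share of an arm responding early, q the share of early responders still responding late, and d the share of early non-responders who respond late.

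- Denominator of subjects tested at the visit: q.
- Whole CMI arm: R·q + (1 − R)·d.
- Difference: (1 − R)(q − d), which is positive whenever q > d and R < 1.
- Ratio when d = 0: 1/R.

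Example: R = 0.6, q = 0.8, d = 0 gives 0.6 × 0.8 = 0.48 for the arm, against 0.80 among those tested. With q = 0.6:

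| R | Tested only | Whole arm, d = 0 | Whole arm, d = 0.2 | Ratio at d = 0 |
|---|---|---|---|---|
| 0.3 | 60% | 18% | 32% | 3.33 |
| 0.5 | 60% | 30% | 40% | 2.00 |
| 0.7 | 60% | 42% | 48% | 1.43 |
| 0.9 | 60% | 54% | 56% | 1.11 |

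Counting untested early non-responders as negative gives R·q, a lower bound. The upper bound, if all of them responded late, is R·q + (1 − R). For R = 0.5 and q = 0.6 the bounds are 30% and 80%.

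**3. Mean frequency**

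A simulation of 400,000 subjects used three visits (two early, one late), each normal with SD 1 and a common pairwise correlation. The true late fall was 0.5 SD. A responder exceeds a cut-off at either early visit, and only responders are tested late. The visit-series change is the late mean among responders minus the second early mean in everyone.

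| Cut-off (SD) | Correlation | R | Change in visit series | Change in the same responders |
|---|---|---|---|---|
| −0.5 | 0.4 | 0.85 | −0.38 | −0.59 |
| −0.5 | 0.7 | 0.80 | −0.25 | −0.56 |
| −0.5 | 0.9 | 0.76 | −0.12 | −0.52 |
| 0 | 0.4 | 0.69 | −0.27 | −0.68 |
| 0 | 0.7 | 0.63 | −0.06 | −0.60 |
| 0 | 0.9 | 0.57 | +0.13 | −0.53 |
| 0.5 | 0.4 | 0.47 | −0.12 | −0.78 |
| 0.5 | 0.7 | 0.42 | +0.19 | −0.64 |
| 0.5 | 0.9 | 0.37 | +0.43 | −0.55 |

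Against the true −0.50, the visit series understates waning in all nine settings and shows a rise in three. Following the same responders errs the other way, by 0.02 to 0.28 SD, because subjects picked on a high early reading regress toward the mean.

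**The case against.** Five points can be made for the plan.

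- **The denominator may already be the whole subset.** The estimand names the CMI subset, and the Table 4 footnote restricts by subject, not by visit. Early non-responders have Day 1, 29 and 43 assessments and so stay in the set. On that reading the example gives 48%, not 80%. This stands: a reader might infer that the table will show 60% and then 80%, but the SAP does not fix that denominator. It does not rescue the mean frequencies, which exist only for those tested.
- **SAP 12.8.2 describes frequencies, not responder percentages by visit.** Correct, so the percentage argument is conditional. The frequency argument is not.
- **Regression to the mean works against apparent durability.** Also correct. A reader might cite it as a further source of overstatement. In the visit series, however, a positive correlation between visits keeps the selected late mean above the late mean of the whole group, so waning is still understated.
- **The restriction is disclosed, and persistence among responders is a legitimate target.** It would be valid if labelled as such. SAP 12.8.2 does not label it.
- **No late comparison of arms is planned.** Protocol 10.3.6 rules out formal immunogenicity hypotheses. A reader might infer a planned late contrast, but the documents contain none. The columns are still shown by vaccine group, so a caution is warranted.

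**Conclusion.** The point holds for the frequency summaries. The stated testing rule combined with the stated summary gives late values conditional on early response, which understate waning when shown beside Day 29/43 values from all tested subjects. The late arms are no longer randomised groups. The direction assumes that a subject's early and late responses are positively correlated.

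For the responder percentage, overstatement follows only if the denominator is subjects tested at the visit and persistence exceeds late new response (q > d). The SAP does not settle the first condition.

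The size cannot be computed from the documents. With d = 0, the ratio of the tested-only percentage to the whole-arm percentage runs from 3.33 at 30% early response to 1.11 at 90%, so the effect is small if nearly all CVnCoV recipients respond early. A general statement that the trial overstates durability would go beyond the text. The impact is confined to exploratory, descriptive endpoints in at most about 200 subjects, and no confirmatory, secondary or safety result is affected. It is worth correcting because duration is a stated goal and the correction is cheap.

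**What to change.** In SAP 12.8.2:

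1. Show the number of subjects tested by arm and visit.
2. Move Day 120/211 frequencies to a separate table of persistence among early responders that also gives the same subjects' Day 29 and Day 43 values. Note that regression to the mean makes this comparison slightly overstate waning.
3. Report Day 120/211 responder percentages on all CMI-tested subjects of the arm who are still in follow-up and not censored at that visit (SAP 10.11 censors immunogenicity data after an authorised vaccine). Count untested early non-responders as non-responders and label the figure a lower bound. Without the follow-up and censoring condition, drop-outs and censored subjects would push the percentage down artificially.
4. State that the late vaccine and placebo columns are descriptive and not to be compared.

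The cost is new table shells and a denominator rule, with no extra assays. The drawback is that late percentages will look less favourable and true late responders will be missed. Protocol 9.1.1.7 and 9.1.1.8 draw late CMI blood without a responder condition, so testing a sample of early non-responders would be an optional, stronger remedy at the price of additional assays.

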9.4 Open-label Endpoints (Scenario A only)

9.4.1 Safety Endpoints

- Occurrence, intensity, and relationship to CVnCoV of SAEs and AESIs collected throughout the trial until the EOT.
- Occurrence of fatal SAEs throughout the trial until EOT.

- Only for Cohort A: CVnCoV-AV: Occurrence of AEs leading to trial discontinuation after the first dose with an AV in the open-label phase until EOT.

9.4.2 Exploratory Efficacy Endpoint

- Occurrence of first episodes of symptomatic virologically-confirmed (RT-PCR positive) cases of COVID-19 of any severity as assessed by the Investigator.

9.5 Estimands

Table 1 presents the study endpoints and corresponding estimands based on the study protocol, Section 4.3.

Table 1: Study Endpoints and Estimands for the Blinded Phase

ENDPOINTS (subject level)	ESTIMANDS (population level)
Primary Efficacy	

 Occurrence of first episodes of virologically-confirmed (RT-PCR positive) cases of COVID-19 of any severity meeting the case definition for the primary efficacy analysis. 	
In naïve evaluable subjects (complying with the definition of Efficacy Analysis Set) at least 15 days following second vaccination:
 
VE = 1 - RR with exact 95% CI
 
Where RR (relative risk) is the ratio of attack rates of COVID-19 cases per 100 person-month in the CVnCoV vaccine group over the placebo group.

Primary Safety	

 Occurrence, intensity and relationship of medically-attended AEs collected through 6 months after the second trial vaccination in all subjects. Occurrence, intensity and relationship of SAEs and AESIs collected through EOT Visit in all subjects. Occurrence of fatal SAEs through EOT Visit in all subjects. 	
In subjects who received at least one dose of CVnCoV or placebo vaccine, the number and percentage of subjects by group reporting at least 1 and at each type (by System Organ Class [SOC]/Preferred Term [PT]) of:
 
 Medically-attended AE in the 6 months after the last vaccination overall, by intensity and by causal relationship to trial vaccine. SAE in the year after the last vaccination overall and by causal relationship to trial vaccine. AESI in the year after the last vaccination overall, by intensity and by causal relationship to trial vaccine. Fatal SAE in the year after the last vaccination.

 Occurrence, intensity and duration of each solicited local AE within 7 days after each trial vaccination in Phase 2b subjects. Occurrence, intensity, duration of each solicited systemic AE within 7 days after each trial vaccination in Phase 2b subjects Occurrence, intensity and relationship of unsolicited AEs occurring within 28 days after each trial vaccination in Phase 2b subjects. 	
In phase 2b subjects who received at least one dose of CVnCoV or placebo vaccine:
 
The number and percentage of subjects by group reporting:
 
 Each solicited local AE within 7 days after each trial vaccination by intensity and overall Each solicited systemic AE within 7 days after each trial vaccination by intensity, by relationship to trial vaccine and overall. At least 1 unsolicited AE, at least 1 grade 3 unsolicited AE and each

ENDPOINTS (subject level)	ESTIMANDS (population level)

 Occurrence of AEs leading to vaccine withdrawal or trial discontinuation through EOT Visit in all subjects. 	
unsolicited AE by SOC/PT occurring within 28 days after each trial vaccination and overall by causal relationship to trial vaccine and overall
 
 At least 1 AE leading to vaccine withdrawal or trial discontinuation in the year after the last trial vaccination 
The mean duration in days by group with standard deviation (SD) of solicited AEs (within the solicited period, total duration).

Key Secondary Efficacy	

 Occurrence of first episodes of virologically-confirmed (RT-PCR positive) cases of moderate to severe COVID-19 meeting the case definition for the primary efficacy analysis. 	
In naïve evaluable subjects (complying with the definition of Efficacy Analysis Set) at least 15 days following second vaccination:
 
$VE = 1 - RR$ with exact 95% CI
 
Where RR is the ratio of attack rates of COVID-19 cases per 100 person month in the CVnCoV vaccine group over the placebo group.

 Occurrence of first episodes of virologically-confirmed (RT-PCR positive) severe cases of COVID-19 meeting the case definition for the primary efficacy analysis. 	
In naïve evaluable subjects (complying with the definition of Efficacy Analysis Set) at least 15 days following second vaccination:
 
$VE = 1 - RR$ with exact 95% CI


 Occurrence of first episodes of virologically-confirmed (RT-PCR positive) cases of "wild type" and "Alpha" SARS CoV 2 strains in SARS CoV 2 naïve subjects. 	
In naïve evaluable subjects (complying with the definition of Efficacy Analysis Set) at least 15 days following second vaccination:
 
$VE = 1 - RR$ with exact 95% CI

Other Secondary Efficacy	

 In subjects ≥ 61 years of age, occurrence of first episodes of virologically-confirmed (RT-PCR positive) cases of COVID-19 of any severity meeting the case definition for the primary efficacy analysis. 	
In naïve evaluable subjects ≥ 61 years of age at randomization (complying with the definition of Efficacy Analysis Set) at least 15 days following second vaccination:
 
$VE = 1 - RR$ with exact 95% CI

 BoD scores calculated based on first episodes of virologically-confirmed (RT-PCR positive) cases of COVID-19 of any severity 	
Where RR is the ratio of attack rates of COVID-19 cases per 100 person-month in the CVnCoV vaccine group over the placebo group
 
In naïve evaluable subjects (complying with the definition of Efficacy Analysis Set) at least 15 days following second trial vaccination:

ENDPOINTS (subject level)	ESTIMANDS (population level)

meeting the case definition for the primary efficacy analysis.
 
 ○ BoD #1 – no disease (not infected or asymptomatic infection) = 0; mild or moderate disease = 1; severe disease = 2. ○ BoD #2 – no disease (not infected or asymptomatic infection) = 0; disease without hospitalization = 1; disease with hospitalization = 2; death = 3. 	$VE_{BOD} = 1 - SV/SP$ with exact 95% CI 
Where SV denotes the ratio of mean BoD score in the CVnCoV group and the mean follow-up time (years) in the CVnCoV group and SP denotes the ratio of mean BoD score in the placebo group and the mean follow-up time (years) in the placebo group.

 ● Occurrence of first episodes of virologically-confirmed (RT-PCR positive) cases of COVID-19 of any severity with symptom onset at any time after the first trial vaccination. 	
In naïve subjects who received at least one dose of CVnCoV or placebo vaccine at any time after the first vaccination:
 $VE = 1 - RR$ with exact 95% CI
Secondary Immunogenicity	

SARS-CoV-2 RBD of S protein antibody responses on Days 1, 29, 43, (57,) 120 and 211:
 
 ● Serum antibodies to SARS-CoV-2 RBD of S protein, ● Occurrence of seroconversion to SARS-CoV-2 RBD of S protein. 
Seroconversion is defined as detectable SARS-CoV-2 RBD of S protein antibodies in the serum of subjects who tested seronegative at baseline.
	
In phase 2b subjects belonging to the IS and evaluable (complying with the definition of per-protocol immunogenicity set):
 
On Days 1, 29, 43, (57,) 120 and 211:
 
 ● Geometric mean of titers (GMT) with 95% CI of SARS-CoV-2 RBD of S protein antibody responses by group and by baseline sero-status and group. 
On Days 29, 43, (57,) 120, 211 (and 393) for subjects seropositive at baseline:
 
 ● Geometric Mean (GM) of Fold Change (FC) from baseline with 95% CI of SARS-CoV-2 RBD S protein antibody responses by group. 
On Days 29, 43, (57,) 120, 211 (and 393) for subjects seronegative at baseline:
 
 ● Number and percentage with exact 95%CI of subjects by group for who a seroconversion is observed (detectable SARS-CoV-2 RBD of S protein antibodies in the serum)

SARS-CoV-2 viral neutralizing antibody responses on Days 1, 29, 43, (57,) 120 and 211:
 
 ● Serum viral neutralizing antibodies to SARS-CoV-2 virus. ● Occurrence of seroconversion to SARS-CoV-2 virus. 
Seroconversion is defined as detectable SARS-CoV-2 viral neutralizing antibodies in
	
In phase 2b subjects belonging to the IS and evaluable (complying with the definition of per-protocol immunogenicity set):
 
On Days 1, 29, 43, (57,) 120, 211 and:
 
 ● GMT with 95% CI of neutralizing antibodies to SARS-CoV-2 virus by group and by baseline serostatus and group

ENDPOINTS (subject level)	ESTIMANDS (population level)

the serum of subjects who tested seronegative at baseline.
	
On Days 29, 43, (57,) 120 and 211 for subjects seropositive at baseline:
 
 • GM of FC from baseline with 95% CI of neutralizing antibodies to SARS-CoV-2 virus by group. 
On Days 29, 43, (57,) 120 and 211 for subjects seronegative at baseline:
 
 • Number and percentage with exact 95%CI of subjects by group for who a seroconversion is observed (detectable neutralizing antibodies to SARS-CoV-2 virus in the serum).
Exploratory Efficacy	

 • Severity assessment of first episodes of virologically-confirmed (RT-PCR positive) cases of COVID-19 meeting the case definition for the primary efficacy analysis 	
In naïve evaluable subjects (complying with the definition of Efficacy Analysis Set) who had a first episode of a virologically-confirmed (RT-PCR positive) case of COVID-19 of any severity meeting the case definition for the primary efficacy analysis:
 
 • The proportions of mild, moderate and severe COVID-19 cases among all cases by severity group

ENDPOINTS (subject level)	ESTIMANDS (population level)

The following endpoints are analyzed as occurring ≥ 15 days following the second trial vaccination (full VE).
 
 • Occurrence of supplemental oxygenation due to COVID-19. • Occurrence of mechanical ventilation due to COVID-19. • Occurrence of hospitalization due to COVID-19. • Occurrence of death due to COVID-19. • Occurrence of death due to any cause. 	
In naïve evaluable subjects (complying with the definition of Efficacy Analysis Set) at least 15 days following second vaccination:
 
Number and percentages by group of subjects who:
 
 • Need supplemental oxygenation due to COVID-19. • Need mechanical ventilation due to COVID-19. • Were hospitalized due to COVID-19. • Deceased due to COVID-19. • Deceased due to any cause.
Exploratory Immunogenicity	

On Days 1, 29, 43, 120, and 211 in PBMCs from up to 200 subjects at selected site(s):
 
 • The frequency and functionality of SARS-CoV-2 RBD of S-specific T-cell response after antigen stimulation by ICS to investigate Th1 response and expression of Th2 markers. • The proportion of subjects with a detectable increase in SARS-CoV-2 RBD of S-specific T-cell response. 
Thereby, testing of samples collected on Day 120 and Day 211 is done only in subjects categorized as T-cell responders on Day 29 and/or Day 43. First testing of samples is performed for a subset of these subjects and might be extended to 200 subjects if T-cell response is detectable.
	
In subjects belonging to the Immunogenicity/Reactogenicity subset and selected to take part of the CMI subset:
 
 • The number and percentage of subjects for whom a SARS CoV-2 RBD of S-specific T-cell response is observed • The number and percentage of subjects with a detectable increase in SARS-CoV-2 RBD of S-specific T-cell response

Table 2: Study Endpoints and Estimands for the Open Label Phase (Scenario A only)

Safety	

 Occurrence, intensity and relationship of SAEs and AESIs collected throughout the trial until the EOT. Occurrence of fatal SAEs throughout the trial until the EOT. Occurrence of AEs leading to trial discontinuation. 	
In subjects who received at least 1 dose of CVnCoV and participate in the open-label phase of the trial:
 
 SAE after the first dose with an AV in the open-label phase until the EOT. AESI after the first dose with an AV in the open-label phase until the EOT. Fatal SAE in the open-label phase through EOT. At least 1 AE leading to trial discontinuation.
Exploratory Efficacy	

 Occurrence of first episodes of symptomatic virologically-confirmed (RT-PCR positive) cases of COVID-19 of any severity as assessed by the Investigator. 	
In naïve subjects from the Open-Label Set (OLS) at any time after the first vaccination:
 $VE = 1 - RR \text{ with exact 95\% CI}$ 
Where RR is the ratio of attack rates of COVID-19 cases per 100 person-month in Cohort A: CVnCoV-AV over Cohort B: CVnCoV only.

